Subjectively, participants will fill out NASA-TLX (NASA Task Load Index) and SOFI (Swedish Occupational Fatigue Inventory) questionnaires. "The NASA task load index (NASA TLX) is a tool for measuring and conducting a subjective mental workload (MWL) assessment. It allows you to determine the MWL of a participant while they are performing a task. It rates performance across six dimensions to determine an overall workload rating. The six dimensions are as follows: mental demand, physical demand, temporal demand, effort, performance, and frustration level. Dimensions will be weighted and a fatigue index score will be calculated with computer software. The SOFI questionnaire is a comprehensive assessment of a participant's subjective perception of fatigue that explores fatigue across 5 domains rated on a sliding 7 point scale: lack of energy, physical exertion,

physical discomfort, lack of motivation, and sleepiness. Participants will complete these questionnaires after providing mask ventilation with each of the two mask ventilation techniques (MVG and 2VE.)

Objectively, fatigue will be measured by recording the changes in tidal volumes achieved per machine delivered breath temporally over the course of 2 three-minute mask ventilation periods.

EXPLORATORY OBJECTIVES:

Exploratory aim 1: One of our exploratory aims is to compare the efficacy (as described above in primary objectives) of the MVG device versus standard 2VE amongst individuals with smaller hands/weaker grip and individuals with larger hands/stronger grip strength.

Exploratory hypothesis 1: Regardless of hand size and grip strength, all individuals will appreciate an increase in tidal volumes with MVG than with standard 2VE, but individuals with smaller hands/weaker grip will appreciate a greater increase in tidal volumes achieved with the MVG device compared to the 2VE technique than individuals with larger hands/stronger grip.

Exploratory aim 2: Our second exploratory aim is to compare the level of difficulty perceived and fatigue (as described above) appreciated while using the MVG device for mask ventilation compared to the standard 2VE amongst individuals with smaller hands/weaker grip strength and individuals with larger hands/stronger grip strength.

Exploratory Hypothesis 2:

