After IRB approval and written informed consents, participating individuals will be categorized to novice or expert groups depending on previously described criteria/years of clinical experience. From these groups, they will be randomized via blindly selecting pieces of paper marked MVG or 2VE. There will be two boxes, one for novices with 16 pieces of paper (8 marked MVG/8 marked 2VE), and one for experts with 16 pieces of paper (8 marked MVG/8 marked 2VE.) Whichever option is selected (MVG or 2VE), the participant will begin with this technique and then switch to the alternative.

ev,The participants will then be guided to the OR simulator where the SimMan Essential patient stimulator (Laerdal Medical Wappingers Falls, NY) (manikin) will be placed supine on aa hospital bed. After this, mask holding technique with MVG device and without (2VE) will be demonstrated by investigators, who will then reviewparticipants' subsequent techniques to ensure consistency throughout the experiment. The parameters for the anesthesia workstation/OR simulator will be checked and confirmed by one or more members of the research team for every participant before the baseline information of participants' demographics and level of experience is recorded. They will be instructed to maintain as tight a seal between the mask/manikin face as possible, that the "patient" only requires mask ventilation during the entire scenario, and that there is no need to perform

additional emergency maneuvers such as chest compressions. The ventilation mask will be connected to an air flow supply via the anesthesia machine ventilator.

Participants will then don their desired sized gloves and perform MVG or 2VE for 30 breaths (approximately 3 minutes) in accordance with the techniques demonstrated previously as an investigator in the room records tidal volumes achieved for each breath onto a data sheet and a separate camera in the OR simulator also simultaneously records the encounter. Tidal volumes will not be recorded until a proper seal is established so participants are aware of what a mask leak feels like. After providing mask ventilation with MVG or 2VE for 30 total breaths, participants are given a 5-minute rest period during which they were to complete the given NASA-TLX and SOFI instruments described above.

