mL/cm H₂O, and the right manikin lung resistance set to 100 cm H₂O/L/sec while the contralateral lung is set to 0 cm H₂O/L/sec. These parameters were designed to mimic the feeling of providing 2VE to difficult patients (obese patient, short neck, obstructive sleep apnea, etc...) while maintaining a tidal volume (TV) of approximately 500 mL \pm 5 mLs. The height of the SimMan Essential Patients Stimulator (manikin) will be adjusted for each participant so that the top edge of the table is flush with the participants' iliac crests. An investigator with a timer will stand approximately 6 feet away from the participants with clear view of the monitors and participants' hands and give out instructions accordingly.

..

Measurements

Baseline information including age, gender and years of experience will be recorded.

Primary outcome: **the difference in the average tidal volume achieved per breath** between the two techniques (MVG and 2VE) in the two groups (novice and expert) as recorded by the anesthesia ventilator over the two 30 breath mask ventilation periods.

Secondary outcomes: Hand fatigue and **difficulty perception**. All participants (both novice and expert groups) will be asked to rate the difficulty of each of the techniques (MVG and 2VE) and express their level of fatigue appreciated by filling out NASA-TLX and SOFI instruments after providing ventilation with each technique.

Exploratory outcome:

Hand fatigue and efficacy of MVG compared to 2VE in regards to participants' hand sizes/grip strength. All participants will have their hand span, palm circumference, and maximum grip force of their dominant hand recorded. This data will be analyzed alongside each participant's answers to the previously described NASA-TLX, SOFI instruments, and gross average tidal volume for each period of ventilation with both techniques.

7) Statistical Analysis

The required sample size for this study was calculated with an online power and sample size calculator for general linear multivariate models (GLIMMMPSE v2.1.0) The parameters used for this study is in JavaScript Object Notation (i.e., JSON) file, which can be uploaded into GLIMMMPSE website and reviewed (URL for GLIMMMPSE program)

A data collection sheet will be used and completed for each included subject. Descriptive statistics will be used for demographic characteristics.

T-paired test model will be used for comparison of the tidal volumes between two groups (MVG and 2VE groups)

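### Could unscripted instructions from the investigator with the timer during the 30 recorded breaths bias the tidal volumes and the fatigue measure?

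*Combined protocol and SAP*

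**What the plan says.** All the relevant procedures are in section 6 (Procedures Involved).

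- **Before recording.** Investigators demonstrate the hold with and without the device, then review participants' "subsequent techniques to ensure consistency throughout the experiment". The briefing is general: "They will be instructed to maintain as tight a seal between the mask/manikin face as possible". Recording is held back: "Tidal volumes will not be recorded until a proper seal is established".
- **During recording.** Participants "perform MVG or 2VE for 30 breaths (approximately 3 minutes") while one investigator writes down the volume of each breath and "a separate camera in the OR simulator also simultaneously records the encounter". The set-up paragraph adds a timekeeper, posted a short distance off, "with clear view of the monitors and participants' hands and give out instructions accordingly".
- **What the breaths are used for.** The Measurements part of section 6 defines the primary outcome as the difference between techniques in average tidal volume per breath over the two 30-breath periods. Section 2 (Objectives) uses the same breaths for objective fatigue: "fatigue will be measured by recording the changes in tidal volumes achieved per machine delivered breath temporally".

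The document contains no script for the investigator with the timer, no explicit ban on coaching and no log of prompts.

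**The concern.** The investigator who gives instructions can see the volumes, the hands and which technique is in use, and section 2 states hypotheses that favour the device and expect novices to gain more. If that person corrected a slipping seal during recorded breaths, the correction would pass straight into the data. If such help went more often to one technique, the paired comparison would carry it. Randomised starting order balances order, not help tied to a technique. A ventilator reading is objective but records a coached breath as faithfully as an uncoached one. The paired t-test removes stable differences between people, not help given in one condition only.

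Fatigue looks more exposed still, because a prompt to tighten the grip could undo the decline that the measure is meant to capture.

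**Working it through.** **1. What is there to instruct?** The ventilator rate is 10 breaths/min and each run has 30 breaths, so 30/10 = 3.0 minutes, which agrees with the protocol's own figure. A session is at least one run, a 5-minute rest and a second run: 3 + 5 + 3 = 11 minutes. It has a start and a stop for each run and an end to the rest. A person holding a timer has those steps to announce. The monitors let that person follow the breath count. The view of the hands is not needed for timing, but it does let an observer see that the assigned hold is in use.

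**2. What do instructions mean elsewhere in section 6?** Where the section spells out what participants are told, it is a standard task direction: keep a tight seal, perform no other emergency manoeuvres, change to the other technique for the second run, position the hand for measurement. None is a correction in response to a leak or a volume.

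**3. Does the review of technique run into the recorded breaths?** The sentence sits after the demonstration and before the workstation check, the briefing, gloving and the run. Its closing words most naturally describe the consistency sought, not the duration of the review. The other reading is possible, so this does not settle the matter. The stated purpose, consistency, points away from helping one technique more than the other.

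**4. What would bias in the primary outcome require?** Suppose a share p of participants is prompted in one technique only, and each prompted run gains g mL on m of its 30 breaths. Then

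shift in the mean paired difference = p × g × m / 30.

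The documents give none of p, g or m. On assumed values:

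| p | g (mL) | m | Shift (mL) | Share of 500 mL |
|---|---|---|---|---|
| 0 (none, or equal in both techniques) | any | any | 0 | 0% |
| 0.25 | 50 | 3 | 1.25 | 0.25% |
| 1 | 50 | 3 | 5 | 1% |
| 1 | 50 | 10 | 16.7 | 3.3% |
| 1 | 100 | 15 | 50 | 10% |

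The answer runs from nothing to 50 mL according to what is assumed, with no document figure to choose between rows and no known sign. The larger rows need sustained coaching of every participant in one technique and of nobody in the other.

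**5. Fatigue.** Assume a steady decline of 1 mL per breath and one prompt after breath 15 that fully restores the starting level. The least-squares slope over 30 breaths goes from -1.0 to about -0.25; a decline of 2 becomes about -0.50. Given equally in both techniques, such prompting would shrink a true slope difference of 2 - 1 = 1 mL per breath to 0.50 - 0.25 = 0.25. That pulls the contrast towards zero and does not favour the device. The result depends on complete restoration and on a slope summary, and the plan specifies neither.

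**The case for a change.** The strongest case for a change is that the gap is real and very cheap to close. No sentence limits speech during breaths 1 to 30, every listed safeguard acts before breath 1, and the investigator is not masked to technique. Two or three sentences restricting calls to start, time and stop would cost no staff, equipment or participants. The possible harm is not trivial either. With no true difference, a 16.7 mL shift in every participant and an assumed SD of paired differences of 50 to 100 mL, a two-sided 5% paired t-test would reject in 45% to 15% of trials with all 32 participants, and in 24% to 10% within a group of 16.

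What stands is the silence itself, and the fact that randomised order would not cure prompting tied to one technique. The rejection rates do not establish a defect. They assume the uniform, one-sided coaching whose existence is in question, and an SD that the documents do not give.

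A ban on correction is also not free. Section 6 wants the runs performed as demonstrated. If correction is forbidden, a participant who drifts from the assigned hold stays in the comparison as though the technique had been used. If it is allowed, the trial measures the technique correctly applied. Either is a defensible target for a manikin study, so the choice is a trade-off.

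**Conclusion.** The concern identifies an unwritten detail and does not call for a change to the plan. The timing-call reading fits the timer, the timed steps and the way instructions are used elsewhere in section 6. Technique work and establishment of the seal are already placed before recording. Bias in the primary difference needs three things together: coaching during recorded breaths, an effect on volume, and imbalance between techniques. The documents show none of them. The camera recording would let the team look back at any run in doubt.

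No size can be given. The 1.25 to 50 mL shifts and the flattened slopes are scale only, resting on assumed frequency, size and persistence of prompts. The conclusion assumes that staff read the timekeeper's role in its ordinary sense. Evidence of technique-specific coaching during recorded breaths would reopen the question.

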After completion of the surveys and the 5-minute rest period, participants were instructed to provide mask ventilation for another 30 machine-delivered breaths utilizing the alternative technique that they had not performed in the previous mask ventilation period. After this period of providing ventilation, participants were again asked to complete another set of NASA-TLX and SOFI instruments in respect to the mask ventilation technique they had just used.

As the final component of the experiment, participants will have their dominant hand measured for hand span, palm circumference, and max grip force produced. Participants will be instructed to spread their fingers on their dominant hand as wide as possible, after which a measuring tape will be used to record the distance from the distal tip of the fifth digit to the distal tip of the first digit in centimeters. Subsequently, participants will be instructed to bring their fingers together, while keeping their first digit fully abducted. From this position, the measuring tape will be used to record the circumference of the widest portion of the palm in centimeters. After these measurements, investigators will demonstrate for the participants, how to grip the dynamometer while having the dorsum of their dominant hand resting against another table from a sitting position. Participants will be given 3 attempts to grip the device as forcefully as possible, from which the average force (kg) will be used as a final number.

All experimental runs will be conducted in the OR simulator at the Center for Patient Safety (CPS) Miller School of Medicine downtown campus of the University of Miami. The OR simulator consists of a SimMan Essential human patient simulator (Laerdal Medical Wappingers Falls, NY) an anesthesia workstation (Datex-Phmeda, GE Healthcare, Little Shalfont, UK,) and an ASL 5000 artificial lung (IngMar Medical, Active Servo Lung, Pittsburgh, PA.)

From the control room, an adjacent room with computers and one-way mirror view of the OR simulator, a CPS technician and another investigator operating the anesthesia workstation will input the following experimental parameters: pressurecontrolled ventilation (PCV) ventilator rate (Rate) of 10 breaths/min, peak inspiratory pressure (PIP) of 37 cm H₂O, Trachea (artificial lung) resistance of 175 cm H₂O/L/sec, compliance of 50

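### Is the primary outcome undermined because the ventilator reading is not named as inspired or expired, and because the 500 mL reference does not obviously follow from the simulator settings?

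*Combined protocol and SAP*

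**What the plan says.** Section 6, under Measurements, takes the primary outcome from average tidal volume per breath "as recorded by the anesthesia ventilator over the two 30 breath mask ventilation periods". Earlier in section 6, an investigator writes down each breath's volume on a data sheet while a camera records the session. Neither place names the inspired or the expired reading. Section 6 also says "Tidal volumes will not be recorded until a proper seal is established".

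The settings in section 6 are "pressurecontrolled ventilation (PCV) ventilator rate (Rate) of 10 breaths/min", "peak inspiratory pressure (PIP) of 37 cm" H2O, "Trachea (artificial lung) resistance of 175 cm" H2O/L/s, compliance 50 mL/cm H2O, and a "right manikin lung resistance set to 100 cm" H2O/L/s with the other lung at 0. The plan explains: "These parameters were designed to mimic the feeling of providing 2VE to difficult patients", while "maintaining a tidal volume (TV) of approximately 500 mL" with a tolerance of 5 mL. It gives no inspiratory time, PEEP or separate expiratory resistance.

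Section 7 compares the two techniques with a paired t-test. Section 2 uses the breath-by-breath volumes as the objective fatigue measure, and the exploratory outcome in section 6 sets average volume against hand size and grip.

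**The concern.** There are two worries.

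- **Direction of the reading.** The device is meant to improve the mask seal. The ventilator sits upstream of the mask, and in pressure control a leak makes it deliver more gas. An inspired reading could therefore rise as the seal worsens, whereas lung and expired volumes fall. If the inspired value were written down, the technique comparison could change sign, and a seal failing with fatigue would show as rising volume. The hand-size and grip analyses would inherit the same fault.
- **The reference value.** 500 ± 5 mL is the only figure for what the set-up should read. If the stated settings cannot put 500 mL into the lung, either something is misdescribed or the 500 mL is some other reading. A reader might then doubt what the ventilator volume measures at all.

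**Working it through.** **Inputs from section 6.** Pressure P = 37 cm H2O; 10 breaths/min, so a cycle T = 60/10 = 6 s; tracheal resistance R = 175 cm H2O/L/s; compliance C = 0.05 L/cm H2O. **Assumed, because not stated:** inspiratory time Ti, PEEP 0, a passive lung, linear resistance, and a ventilator that holds its pressure.

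**Step 1: can 500 mL be reproduced on the plain reading?** Take one resistance in both directions, with breaths at equilibrium and Te = T − Ti:

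V = C·P·(1 − e^(−Ti/RC))·(1 − e^(−Te/RC)) / (1 − e^(−T/RC))

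Here RC = 175 × 0.05 = 8.75 s and C·P = 0.05 × 37 = 1.85 L.

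- Ti = 2 s: 1850 × 0.2043 × 0.3669 / 0.4963 = 279.5 mL.
- Ti = 3 s: 1850 × 0.2903² / 0.4963 = 314 mL.
- Ceiling over any Ti and any compliance: P·T/(4R) = 37 × 6 / (4 × 175) = 0.317 L.
- With the two lung resistances (100 and about 0) added: 265 to 309 mL for Ti of 2 to 3 s.

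So 500 ± 5 mL is not reproduced on this reading; it is about 1.6 times the ceiling (500/317).

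**Step 2: does the ceiling follow from the stated settings alone?** No. It needs two further conditions.

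*Equal resistance in expiration.* The plan gives one value and no direction. With inspiratory resistance 175, C = 50 mL/cm H2O and a separate expiratory resistance Re, the first exponential keeps 175, the second uses Re, and the denominator becomes one minus their product.

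| Ti | Re | Equilibrium volume |
|---|---|---|
| 2 s | free expiration | 378 mL |
| 2.76 s | free expiration | 500 mL |
| 3 s | free expiration | 537 mL |
| 3 s | 38 | about 500 mL |
| 4 s | 57 | about 500 mL |

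At Ti = 2 s, 500 mL is out of reach in every variant, because flow cannot exceed 37/175 = 0.211 L/s, or 423 mL in 2 s.

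*Equilibrium.* From an empty lung, the first breath is 1850 × (1 − e^(−3/8.75)) = 537 mL at Ti = 3 s, falling to 321 mL by the sixth. The mean of 30 breaths from rest is 286 mL (Ti 2 s) or 329 mL (Ti 3 s), and 347 mL with C = 100 and Ti 3 s. This alone does not sustain 500 mL, but it shows that 317 mL is not an absolute maximum.

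A sealed ventilator reading could also include gas compressed upstream: (500 − 317)/37 = 4.9 mL/cm H2O would close the gap.

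**Step 3: where is 500 mL used?** It appears once, as a description of the set-up. The primary outcome, the paired t-test, the fatigue measure and the exploratory outcome do not refer to it. Section 6 has the workstation parameters checked for every participant, and both techniques run under the same settings.

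**Step 4: what would the unnamed reading do?** In one illustrative case (Ti 2 s, circuit resistance 2, PEEP 0, leak always open), a 12 L/min leak moves the inspired reading from 276 to 666 mL, lung volume from 276 to 273 mL and expired volume from 276 to 271 mL. Over a wider set of assumed conditions (Ti 2 or 3 s, circuit resistance 2 or 20, PEEP 0 or 5, three leak patterns), the same leak changes the inspired reading by +308 to +588 mL and the expired reading by −3 to −136 mL. So the inspired reading moves the wrong way and the expired reading the right way. None of these leak conditions is in the documents.

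**Step 5: which reading does the plan imply?** Section 2 predicts larger volumes with the device, and the background attributes this to a better seal. That holds only for a volume that falls with leak. The background compares one- and two-handed techniques by expired volume. All of this points to the expired reading.

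**The case for a change.** The best argument for acting is that the primary outcome should not rest on inference. A modern ventilator may show both readings, an investigator writes one of them down, and the wrong choice would reverse the sign of the result rather than add noise. Common settings and within-participant pairing give no protection, because leak is the very thing that differs between techniques. Requiring a seal before recording does not help either: the plan does not say how the seal is judged, and leak can develop during the 30 breaths. Each route to 500 mL also needs a setting that the plan does not give, and the remedy would take only a sentence or two and a short sealed run.

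Much of this stands. The reading is unnamed, and on the plain reading the settings and the 500 mL do not agree; the sponsor would do well to reconcile them in the study file. What does not stand is the step from there to a defect. The harm requires the inspired value to have been recorded. Nothing indicates that it was, and the plan's own logic points the other way. The leak figures show what could happen under assumed conditions, not the size of an error in this plan. Nor is it true that either a setting is misstated or 500 mL is not lung volume: with a lower expiratory resistance and a longer inspiratory time, every stated figure can be correct.

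**Conclusion.** No change to the design, outcome or analysis follows. The missing word is a gap that analysts would fill sensibly with the expired reading, for which the direction of the comparison is right; the data sheet, which is not in the documents, may already name it. The settings do not reproduce 500 ± 5 mL on their plain reading (280 to 314 mL for inspiratory times of 2 to 3 s, ceiling 317 mL), but that result needs equal resistance in both directions and equilibrium, and about 500 mL is attainable without contradicting any stated figure. I take no view on which setting, if any, is misdescribed. Since the 500 mL figure is not used in any analysis, reconciling it would alter no result.

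This rests on a linear, passive lung model with pressure held, and on the expired volume being the one recorded. Evidence that inspired volume had been written down would reopen the first point; the 500 mL question would still be one of description only.

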Title: Improvement of Manual Ventilation Efficacy with Ventilation Grip Device: a manikin study

Document Date: 21 April 2022

Study NCT Number: NCT05059366

1) **Protocol Title**

Improvement of Manual Ventilation Efficacy with Ventilation Grip Device: a manikin study.

Principal Investigator: [name]

Setting: Center for Patient Safety, University of Miami Miller School of Medicine

2) **Objectives***

PRIMARY OBJECTIVES:

Primary aim: Our primary goal is to assess the efficacy of the Mask Ventilation Grip (MVG) device via comparison of the average tidal volumes achieved during respiration using the MVG device compared to the standard two-handed V-E technique(2VE),by measuring the average tidal volume(s) achieved as well as changes in the obtained tidal volumes over a duration of two three-minute cycle in both experienced (expert) and inexperienced (novice) clinicians

Primary hypothesis: Specifically, we hypothesize that use of the MVG device when providing two-handed mask ventilation will improve the average tidal volumes achieved compared to the standard 2VE technique in both expert and novice groups in a manikin simulation setting with novices appreciating a greater increase in average tidal volume than experts

SECONDARY OBJECTIVES:

Secondary aim 2: Our second aim is to investigate the level of perceived difficulty and fatigue experienced while using of the MVG device versus the standard 2VE technique. in both expert and novice groups

Secondary hypothesis: Providing mask ventilation to a manikin is easier (subjective perception of difficulty) when using the MVG device compared to the standard 2VE technique in both groups, with the novice group demonstrating a greater ease to ventilate. Hand-fatigue is reduced by using the ventilation grip device compared to the standard 2VE technique in both expert and novice groups with the novice group appreciating a greater reduction in fatigue with the MVG compared to 2VE than the expert group.

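### Section 7 names no test for the part of the primary hypothesis that says novices gain more from the MVG device than experts

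*Combined protocol and SAP*

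**What the plan says.** Section 2 of the combined protocol and SAP states, as the primary hypothesis, that the MVG device improves average tidal volume "in both expert and novice groups in a manikin simulation setting with novices appreciating a greater increase in average tidal volume than experts". That is three statements: a gain in experts, a gain in novices, and a larger gain in novices.

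The primary outcome (section 6, Measurements) is the difference in average tidal volume per breath "between the two techniques (MVG and 2VE) in the two groups (novice and expert".

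The design can supply the comparison. Section 5 describes a mixed repeated-measures study. In section 6 each participant uses both techniques: "Whichever option is selected (MVG or 2VE), the participant will begin with this technique and then switch to the alternative". Allocation is by slips drawn within expertise group: "There will be two boxes, one for novices with 16 pieces of paper (8 marked MVG/8 marked 2VE", with a matching box for experts.

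Section 7 contains three things:
- a sample-size statement citing "an online power and sample size calculator for general linear multivariate models (GLIMMMPSE v2.1.0", with its parameters held in a separate file;
- "Descriptive statistics will be used for demographic characteristics";
- the one inferential sentence, "T-paired test model will be used for comparison of the tidal volumes between two groups (MVG and 2VE groups".

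In that last sentence the two groups are the techniques, not the novices and experts.

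**The concern.** The third statement is a contrast between independent groups of a within-person difference, that is, a technique-by-expertise interaction. A paired t-test asks only whether one mean difference is zero. If the plan is followed as written, the first two statements can be tested (by group, as the outcome wording suggests), but the third has no stated analysis. How to judge it would then be decided after the data are seen, for a claim that sits in the primary hypothesis. The easiest improvisation is to note that the device effect was significant in one group and not in the other, and that is a poor guide to which gain is larger.

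**Working it through.** **No figure to reproduce.** The text gives no alpha, power, expected gain or SD.

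**Inputs.**
- 16 novices and 16 experts: implied by the slips in section 6.
- Two-sided alpha 0.05: assumed.
- Normally distributed differences with the same SD in both groups: assumed. Effects are in units of that SD, the SD of the within-participant MVG minus 2VE difference, and are shown over a range.

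**Step 1: what each test estimates.** Let δN and δE be the mean gains in novices and experts.
- Pooled paired test: (δN + δE)/2.
- Paired test by group: δN and δE, each against zero.
- Third statement of the hypothesis: δN − δE.

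Neither form of the paired test estimates or tests δN − δE. Simulation (20,000 runs) shows that the pooled test cannot tell the hypothesised pattern from its reverse:

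| True gain, novice / expert (SD) | Pooled paired test rejects | Direct comparison rejects |
|---|---|---|
| 0.50 / 0.50 | 78% | 5% |
| 0.75 / 0.25 | 76% | 28% |
| 0.25 / 0.75 | 77% | 28% |

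**Step 2: if someone inferred the contrast from two by-group p-values.** With equal true gains, let p be the power of one paired test with n = 16 (noncentral t, noncentrality d√16). The chance of significance in novices only is p(1 − p):

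| Common gain d (SD) | p | p(1 − p), from unrounded p |
|---|---|---|
| 0.2 | 0.113 | 0.100 |
| 0.3 | 0.202 | 0.161 |
| 0.4 | 0.322 | 0.218 |
| 0.5 | 0.465 | 0.249 |
| 0.6 | 0.612 | 0.237 |
| 0.75 | 0.801 | 0.160 |
| 1.0 | 0.962 | 0.037 |

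A direct Welch comparison wrongly favours novices in about 2.5% of trials throughout (2.4 to 2.5%, 200,000 runs). The rule also fails in the other direction. With true gains of 2.0 SD in novices and 1.0 SD in experts, the novices-only pattern appears in 4% of trials, because both tests are usually significant. The direct comparison detects that difference in 78%.

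**Step 3: the direct comparison.** Standard error of the difference in gains = SD × √(1/16 + 1/16) = 0.354 SD. With 30 df, the 95% CI half-width is 2.042 × 0.354 = 0.72 SD. Power (noncentral t) is 28%, 54% and 78% at gaps of 0.5, 0.75 and 1.0 SD, and 80% power needs a gap of 1.02 SD.

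**Step 4: non-overlap of the by-group 95% CIs.** Each half-width is about 2.131/√16 = 0.533 SD, so non-overlap needs an observed gap of about 2 × 0.533 = 1.07 SD, against 0.72 SD for the direct test. In simulation (200,000 runs) it wrongly favours novices in about 0.3% of trials. It detects gaps of 0.5, 1.0 and 1.5 SD in 7%, 45% and 88%, against 27%, 78% and 98% for Welch.

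**The case against.** The best defence is that the surrounding text already points to the right analysis. The design is called mixed, the outcome is worded by expertise group, and the sample-size tool is built for general linear multivariate models, which can carry an interaction. Part of this stands: analysis by group is the natural reading, although section 7 does not say so. The rest does not fill the gap. The calculator is cited for sample size only, and the sentence on analysis names a different and simpler method.

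Three stronger readings are tempting, and the documents support none of them.
- A reader might infer that the trial could draw no valid conclusion about the third statement, or could only set two p-values side by side. Paired analyses by group also yield a mean gain and a CI for each group, and non-overlap of those intervals is a valid, conservative inference (step 4). It is inefficient, and section 7 does not mention intervals.
- A reader might take 16 to 25% as the error rate of the plan. It is the error rate of an inference that the protocol nowhere proposes.
- A reader might infer that the study was sized for the wrong hypothesis. The calculator's input file is not in the documents, so which hypothesis was powered cannot be known.

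**Conclusion.** The point holds as an omission in the analysis section: one of the three statements in the primary hypothesis has no named test, and the test that is named does not address it. This follows from what a paired t-test is and needs no assumed effect size. The within-group comparisons are not undermined.

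The sizes quoted do depend on assumptions: 16 per group with full data, two-sided 0.05, and effects in SD units, because the documents give no SD with which to convert them to millilitres. It should be fixed before analysis. The change is small, but it concerns a primary claim.

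**What to change.** Add to section 7:
1. For each participant, compute the MVG minus 2VE difference in mean tidal volume.
2. Estimate and test the mean difference separately in novices and in experts, each with a 95% CI, as the primary outcome is worded.
3. Test the greater gain in novices by a two-sample Welch comparison of these differences, or by the equivalent technique-by-expertise interaction. Report the difference in gains with its 95% CI.
4. State that this contrast will not be inferred from significance in one group and not the other, and that a non-significant result will not be read as equal gains.

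The cost is a few sentences and a few lines of code on data already planned; no extra participants are needed to make the statement testable. The drawback is precision. With 16 versus 16, power is only 28% at a gap of 0.5 SD, and 80% power there would need about 64 per group.

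Two additions are not needed for this repair. Adjusting for starting technique is optional: with 8/8 order and full enrolment there is no period bias, so it brings only a minor gain in efficiency. A stepwise multiplicity rule over the three tests for partial claims is a separate trade-off. For example, Holm adjustment would lower the chance of claiming a gain in both groups from 64% to 47% at gains of 0.75 SD in each.
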